1.0 Objectives

- 1.1 The primary objective of this study is to evaluate the efficacy of a combination of capecitabine and radiation therapy with or without curcumin in locally advanced rectal cancer as assessed by pathological complete response rate.
- 1.2 Secondary objectives include:
 - 1.2.1 To determine downstaging, local control, disease-free survival and overall survival rates.
 - 1.2.2 To determine serum and rectal tumor tissue pharmacology of curcumin and its metabolites in the above patients and its correlation with clinical response.
 - 1.2.3 To identify surrogate molecular markers for curcumin effects.
 - 1.2.4 To correlate serum cytokine levels with quality of life in patients receiving this therapy.

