9.0 Correlative Studies

9.1 Clinical pharmacology studies (optional)

9.1.1 Blood samples (20 ml) will be collected in lavender top tubes at the Endoscopy suite during the second week of CRT and processed as follows. This will be performed pre-dose and 1-hour +/- 10 minutes post-dose of curcumin or placebo. A third of the sample will be centrifuged immediately (1500 x g for 15 min at 4°C). The plasma is removed and stored at -20°C. The samples will be shipped in the frozen state for storage until ready for analysis in the core pharmacology lab. The remaining two-thirds of the sample will be transferred into a 50 cc conical tube to which is added an equal volume of PBS. The tube is inverted 10 times. The diluted blood is transferred to another 50 ml conical tube that contains an equal volume of Ficoll-Paque using a transfer pipette. The diluted blood is carefully laid over the Ficoll-Paque at room temperature. The tube is capped and centrifuged (700 x g for 30 min) at room temperature using a swinging bucket rotor. Cells (peripheral blood mononuclear cells, PBMC) are obtained at the resulting interface, transferred to another tube and washed once with PBS. After centrifugation, cells are then resuspended, and samples saved for immunocytochemical analyses.

9.1.1.1 Plasma curcumin, curcumin glucuronide, curcumin sulfate, demethoxycurcumin, and bisdemethoxycurcumin will be measured using high-performance liquid chromatography and mass spectrometry.

- 9.1.1.2 Curcumin and its metabolites will be expressed in micrograms of drug per milliliter of plasma.
- 9.1.1.3 Results will be expressed as means +/- standard deviations.
- 9.1.1.4 PBMC will be used for immunocytochemical analysis.
- 9.1.2 Biopsies (tumor) will be obtained during the second week of chemoradiation therapy and at restaging. Surgical specimen will also be collected.
 - 9.1.2.1 Biopsy tissue and surgical tissue will be immediately frozen in liquid nitrogen and stored at -80°C. The tissue will be homogenized (liquid nitrogen cooled mortar and pestle, cold spatula transfer to cooled eppendorf, cryocentrifuged, digested, homogenized in ultrasonic homogenizer) and then analyzed for targets (curcumin and its metabolites) as noted above.
 - 9.1.2.2 Curcumin and its metabolites will be expressed in micrograms of drug per milligram of wet tissue weight.
 - 9.1.1.3 Results will be expressed as means +/- standard deviations.

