9.3 Surrogate marker analyses

These will be performed by personnel who are blinded to the treatment status of the patients.

Fresh frozen tumor from biopsy and surgical specimens will be processed for correlative studies as noted below:

- 9.3.1 A portion of tumor tissue will be snap frozen for measurement of drug levels as noted in 9.1.2.
- 9.3.2 A portion will be frozen for Western blot analysis, electrophoretic mobility shift assay, and microarray analysis. Tissue will be homogenized and probed with specific antibodies for Western blot analysis of key proteins including bcl-2, bax, PARP, VEGF, cyclin D1, and cox-2. Nuclear extracts will be prepared for EMSA of NF- κ B DNA-binding.
- 9.3.3 Another portion will be processed for immunohistochemical analysis including p65, p-stat3, cox-2, VEGF, Ki-67, and CD31 evaluation.
- 9.3.4 The remainder will be frozen for further analysis.
- 9.3.5 Labeled sterile Nunc tubes will be used to store tissue samples.
- 9.3.6 All tissue not mentioned above will be routinely processed as per the pathology department.

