For the experimental treatment we will compare the concentration of curcumin in the tumor with the curcumin concentration levels in serum. We will find the difference in curcumin concentration levels in tumor and serum for each patient (tumor – serum), and then we will use a paired t-test to determine whether the mean difference is statistically significant.

For the experimental treatment we will estimate the correlation between the curcumin level in tumor tissue and 1) NF- κ B activity, and 2) pCR. We will also estimate the correlation between the curcumin level in serum and these same variables.

We will use a logistic regression model with pCR as the dependent variable to assess the association between pCR and NF- κ B activity and treatment.

We will also compare between treatment groups changes in selected components of known relevant pathways in both normal and tumor tissue. These include bcl-2, bax, PARP, VEGF, cyclin D1, p-stat3, Ki-67, CD31 and cox-2.

Quality of Life and Toxicity

Patients will complete validated quality of life (QoL) instruments at baseline and weekly during chemoradiation. These instruments include the MD Anderson Symptom Inventory-Gastrointestinal (MDASI-GI) and Brief Fatigue Inventory (BFI). A panel of cytokines (IL-1 β , IL-8 and TNF- α) will be assayed at these same evaluation times. We will estimate the correlation between the various cytokine levels and the various QoL instrument scores.

We will also compare changes from baseline in cytokine levels between treatment groups using a repeated measures analysis of variance model. We will construct side-by-side boxplots of changes from baseline in cytokine levels by treatment group for each evaluation time. We will also construct side-by-side boxplots of changes from baseline of QoL instrument scores by treatment group for each evaluation time.

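### Must Section 13 say which tumour specimen supplies the curcumin level that is related to pCR?

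*Combined protocol and SAP*

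**What the plan says.** Objective 1.2.2 is "To determine serum and rectal tumor tissue pharmacology of curcumin and its metabolites in the above patients and its correlation with clinical response". Three analyses in Section 13, Correlative Studies, use tumour values:

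- a paired comparison in the curcumin arm: "We will find the difference in curcumin concentration levels in tumor and serum for each patient";
- correlations in the curcumin arm: "For the experimental treatment we will estimate the correlation between the curcumin level in tumor tissue" and, separately, NF-κB activity and pCR;
- a model of pCR on NF-κB activity and treatment: "We will use a logistic regression model with pCR as the dependent variable".

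None of them names a specimen. On collection, Section 9.1.2 says "Biopsies (tumor) will be obtained during the second week of chemoradiation therapy and at restaging. Surgical specimen will also be collected". On assay, 9.1.2.1 says "Biopsy tissue and surgical tissue will be immediately frozen in liquid nitrogen" "and then analyzed for targets (curcumin and its metabolites) as noted above". Section 9.3 does not separate the sources either: "Fresh frozen tumor from biopsy and surgical specimens will be processed for correlative studies as noted below".

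The timing is found elsewhere. Section 5.4 continues the capsules for six weeks beyond chemoradiation. Section 8.0 puts most operations one to three weeks after that. Section 7.5 makes the week-2 biopsy and blood draw optional. The calendar in 7.12 marks the Section 9.1 pharmacology row at week 2 only.

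**The concern.** pCR is read from the surgical specimen. On its usual meaning (no residual tumour, which the documents do not spell out), a patient with pCR has no surgical tumour to assay. Whether a surgical tumour value exists would then depend on the outcome it is to be correlated with. Surgical tissue is also mostly off-drug, while the week-2 biopsy is on-drug.

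Two failures are conceivable. With surgical tumour alone, every contributing patient has pCR = 0, and neither the correlation nor the logistic model can be estimated. With surgical values standing in for missing week-2 biopsies, or averaged with them, low off-drug values would enter only for non-responders. That could create an apparent link between higher tumour curcumin and pCR where none exists. The analysis serves a named secondary objective, and a false exposure-response signal could mislead later development.

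**Working it through.** The plan states no sample size, power or error rate for these correlations, so there is no figure of its own to reproduce. The check has two parts.

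**1. Which specimen do the documents imply?**

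| Specimen | Timing | On drug? | Matched blood? | Calendar |
|---|---|---|---|---|
| Pre-treatment biopsy | before enrolment (6.1.1.5) | no | no | listed |
| Week-2 biopsy | after at least 5 fractions (7.5) | yes | yes | listed, optional |
| Restaging biopsy | 6–12 weeks after chemoradiation, i.e. 0–6 weeks after planned end of dosing | mostly no | no | not listed |
| Surgical tissue | mostly 6+1 to 6+3 = 7–9 weeks after chemoradiation | mostly no | no | not listed |

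The calendar's pharmacology row refers to Section 9.1, which holds both the blood assay (9.1.1) and the tissue assay (9.1.2), and it is marked at week 2 only. Blood for pharmacology is drawn only then. The tumour-minus-serum difference can therefore be matched in time only with the week-2 biopsy. The correlation follows it directly and uses the same two quantities, tumour level and serum level.

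**2. How large is the harm if another specimen is used?**

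*Surgical tumour only.* Expected pCR counts, from the rates and arm sizes in Section 13:

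- curcumin arm: 30 × 0.18 = 5.4 to 30 × 0.36 = 10.8;
- placebo arm: 15 × 0.18 = 2.7.

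None of these patients would contribute a value. The outcome would not vary and no coefficient would exist, so the analyst would see the failure at once.

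*Substitution or averaging.* Simulation with no true association: 30 curcumin patients, 11 with pCR; week-2 level lognormal with mean 1 and CV 50%; each patient has a week-2 biopsy with probability 50%; surgical level = r × an independent lognormal with the same CV. Entries are the mean point-biserial correlation and the two-sided 5% rejection rate. Uptake, CV and r are assumptions; the documents give none of them.

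| Who supplies surgical values | r | Week-2 only | Week-2, else surgical | Mean of available |
|---|---|---|---|---|
| every non-pCR patient | 0.1 | 0.00 / 4% | 0.33 / 36% | 0.64 / 94% |
| every non-pCR patient | 0.5 | 0.00 / 4% | 0.22 / 21% | 0.41 / 55% |
| every non-pCR patient | 1.0 | 0.00 / 4% | 0.00 / 5% | −0.01 / 6% |
| non-pCR patients who gave a week-2 biopsy | 0.1 | 0.00 / 4% | 0.00 / 4% | 0.54 / 60% |
| half of non-pCR patients, at random | 0.1 | 0.00 / 5% | 0.24 / 17% | 0.40 / 43% |
| all patients (tumour bed assayed in pCR, same level) | 0.1 | 0.00 / 5% | 0.00 / 5% | 0.00 / 5% |

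With every non-pCR patient supplying surgical tissue and r = 0.1, varying uptake over 50–75%, CV over 50–100% and pCR count over 5 or 11 gives 0.09 to 0.33 for substitution and 0.33 to 0.64 for averaging. Week-2 values alone show no bias in any cell.

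**Decision rule.** The two-stage rule uses only pCR counts in the curcumin arm: at least 3 of 16 to continue, then at least 9 of 30. Exact binomials give a stopping probability of 0.430 at 18% and 0.038 at 36%, and an actual significance level of 0.0746, in line with the stated 0.43, 0.04 and 7.5%. Tissue values play no part in it.

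**The case for a change.** The strongest case for a change is that the text does leave the choice open. No sentence carries week 2 into the pCR analyses, and 9.1.2.1 assays surgical tissue regardless. Because the week-2 biopsy is optional, some patients may have only surgical tissue, which invites substitution once pCR is known. Averaging stays biased even when only week-2 donors give surgical tissue (0.54), and a few sentences would close the gap without new samples.

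That the specimen is unnamed stands. So does the direction of the bias under either pooling rule if curcumin has washed out. But no passage prescribes substitution or averaging, so these figures describe hypothetical misuse. The larger substitution figures also need non-pCR patients without a week-2 biopsy to supply surgical tissue, although all of Section 9.1 is headed optional. If tumour-bed tissue were frozen and assayed before histology, pCR patients would have values too; tissue type would then be confounded with pCR, which is a different problem from the missing values simulated here.

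For NF-κB the documents leave open the pre-treatment as well as the week-2 biopsy. Both precede the pCR reading, so neither makes availability depend on the outcome. The choice affects interpretation, not validity.

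The smaller points are real but editorial: serum is written where plasma is assayed; the pre-dose or 1-hour draw is not named; the restaging biopsy is missing from 7.9–7.11 and the calendar; and tissue and plasma units differ. On units, 1 µg/mg is 1,000 µg/g, or about 1,000 µg/mL at an assumed density of 1 g/mL, and no analyst would subtract across that factor unnoticed.

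**Conclusion.** No change to the plan is needed. Section 13 omits a detail, but no rule it states gives a wrong result. The schedule points to the week-2 biopsy for curcumin. That is the specimen a sensible analyst would use, and with it the bias is zero in every setting examined. The most damaging single-specimen choice, surgical tumour alone, cannot go unnoticed because nothing could be estimated.

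The remaining risk is a pooled tumour value. Depending on assumed uptake, variability, washout and who supplies surgical tissue, it runs from no bias to a mean spurious correlation of 0.33 under substitution and 0.64 under averaging. It arises only if an analyst adopts a rule that the plan does not contain. The analysis is correlative, is worded as estimation with no stated error rate, and would be imprecise in any case: at 50% uptake with 11 pCR, about 5.5 pCR and 9.5 non-pCR week-2 values. The primary pCR decision is unaffected. Recording the specimen, draw, unit and number of contributing patients when results are reported is ordinary analyst practice.

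This conclusion rests on reading the calendar's pharmacology row as covering tissue as well as blood, and on the usual meaning of pCR.

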macrophages and natural killer cells and modulation of lymphocyte-mediated function (69, 70). Therefore, the exact mechanism of action of curcumin remains inadequately explained. However, the most consistent finding is that curcumin induces apoptosis. This may be mediated by impairment of the ubiquitin proteasome pathway (71), upregulation of proto-oncoprotein Bax (72, 73), activation of caspases and induction of Fas receptor aggregation in a FasL dependent manner (73), and the generation of free radicals (74).

The NF- κ B pathway:

NF- κ B resides in the cytoplasm of cells in the inactive state in a complex with inhibitors of κ B (I κ Bs). NF- κ B is activated by phosphorylation of I κ B- α at two serine residues (Ser-32 and -36) or, less frequently, at a tyrosine residue (Tyr-42) by I κ B kinases leading to its ubiquitination and degradation by the proteasome complex. This leads to release of the active NF- κ B, which translocates to the nucleus and binds to its consensus sequence in the promoter or enhancer region. This further leads to transcription of a wide variety of anti-apoptotic genes and other pleiotropic effects. The usual triggers for NF- κ B activation are cytokines such as IL-1 and TNF- α , bacterial or viral infections, growth factors acting via the atypical kinase (Akt) pathway, and stress (including reactive oxygen intermediates and ionizing radiation). The effector proteins include acute phase reaction proteins, cytokines, adhesion molecules and feedback regulatory proteins that moderate the NF- κ B response. In colorectal cancer in particular, cyclo-oxygenase-2 (cox-2) is a key mediator of tumor progression whose expression is also mediated by NF- κ B.

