- 5.2.4 Dose: CTV1 will be treated to a dose of 45 Gy. This will be followed by a boost to CTV2 with a dose of 5.4 Gy. At the discretion of the treating radiation oncologist, up to an additional 3.6 Gy may be administered during the boost. All plans will be generated using 3D conformal techniques. At the discretion of the radiation oncologist, an intensity-modulated radiation therapy (IMRT) plan may be generated.
- 5.2.5 Fractionation: Radiotherapy will be delivered in 180 cGy once daily fractions for 28 fractions.
- 5.2.6 Dose constraints: Dose to the femoral heads will be limited to 50 Gy. The volume of small bowel getting > 45 Gy will be minimized. Dose heterogeneity will be less than 10%.
- 5.2.7 Radiotherapy will be interrupted for treatment related > Grade 2 non-hematological toxicity until it resolves to grade 1, then continued. If radiotherapy is interrupted, then capecitabine will also be interrupted. Please note that for any event which is apparent at baseline, the interruption will apply according to the corresponding shift in toxicity grade if the investigator feels it is appropriate (e.g. if a patient has grade 1 asthenia at baseline which increases to grade 2 during treatment, this will be considered as a shift of 1 grade and treated as a grade 1 toxicity for radiation interruption purposes).

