6.0 Pretreatment evaluation

6.1 Prior to Study Enrollment:

- 6.1.1 Patients must have the following tests before study enrollment:
 - 6.1.1.1 Blood chemistries (bilirubin, alkaline phosphatase, ALT, AST, BUN, creatinine, phosphorus, calcium, glucose, total protein, albumin, and electrolytes [sodium, potassium, carbon dioxide, and chloride], Complete blood count (CBC: hemoglobin, hematocrit, WBC with differential blood cell counts (neutrophils, bands, lymphocytes, monocytes, eosinophils, basophils) and platelets), carcinoembryonic antigen (CEA), urinalysis, all within 10 days of enrollment. PT and INR will be done if patient is on coumadin and phenytoin levels will be checked in patients on phenytoin.
 - 6.1.1.2 Urine pregnancy test within 72 hours of enrollment in women of child-bearing potential
 - 6.1.1.3 Radiographic studies (CXR or chest CT; CT of the abdomen and pelvis) within 30 days of enrollment
 - 6.1.1.4 Colonoscopy within 3 months of enrollment and flexible sigmoidoscopy/ EUS within 30 days of enrollment
 - 6.1.1.5 Endoscopic biopsy prior to study enrollment
- 6.1.2 After consent but prior to initiating chemoradiation therapy, additional tests for research purposes include:
 - 6.1.2.1 MD Anderson symptom inventory (MDASI) questionnaire gastrointestinal module (appendix F)
 - 6.1.2.2 Brief Fatigue Inventory (BFI) (appendix E)
 - 6.1.2.3 Blood collection for cytokine analysis

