9.2 Cytokine assays (optional)

These will be performed by personnel who are blinded to the treatment status of the patients.

- 9.2.1 Blood will be collected in lavender top tubes at study initiation and weekly during chemoradiation for cytokine analyses. This will be stored in the laboratory until bunched samples can be analyzed in the core cytokine lab. The cytokines assayed will include IL-1b, IL-8 and TNF-a.

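### The between-arm cytokine comparison subtracts the collected baseline without adjusting for it; a baseline covariate can sharpen the week-averaged arm effect, usually at little cost

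*Combined protocol and SAP*

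**What the plan says.** Section 13.0, under Quality of Life and Toxicity, sets out the between-arm analysis: "We will also compare changes from baseline in cytokine levels between treatment groups using a repeated measures analysis of variance model". It adds a display by visit: "We will construct side-by-side boxplots of changes from baseline in cytokine levels by treatment group for each evaluation time". It does not say whether the comparison of interest is the difference averaged over weeks, the difference at a given week, or the group-by-week interaction. It gives no SD, correlation, effect size or power for cytokines.

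The baseline value will exist for patients who give samples. Section 6.1.2, after consent and before chemoradiation, lists "Blood collection for cytokine analysis", and section 9.2.1 says "Blood will be collected in lavender top tubes at study initiation and weekly during chemoradiation for cytokine analyses". Section 9.2 and the study calendar mark the cytokine work as optional. No analysis in section 13.0 names a baseline covariate.

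**The concern.** Subtracting the baseline is one way of using it, and it amounts to assuming that a patient who starts one unit higher will on average stay one unit higher. If the true slope is below 1, subtraction over-corrects and adds baseline noise to the comparison; if it is above 1, subtraction under-corrects. A covariate lets the data set the slope.

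What is at stake is precision. There are at most 45 patients (15 placebo, 30 curcumin), and optional sampling may leave fewer. The same gap between the slope and 1 determines how much of a chance baseline imbalance between arms stays in the estimate.

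**Working it through.** **Plan's own figure.** None exists for this comparison, so there is nothing to reproduce.

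**Inputs from the documents.** 15 v 30 patients (section 13.0). Section 5.2.5 says "Radiotherapy will be delivered in 180 cGy once daily fractions for 28 fractions"; at five fractions per week, 28/5 = 5.6 weeks, so five or six weekly draws.

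**Inputs assumed.** Baseline SD 1; follow-up SD k at every week; one correlation rho between any two times (compound symmetry); m = 6 weekly values; every patient sampled. The documents give neither rho nor k, so both are varied.

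**Formulas, arm effect averaged over m weeks.** Let A = (1 + (m-1)rho)/m. Each variance is multiplied by (1/15 + 1/30).

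- Change score: k²A + 1 - 2k·rho
- Baseline-adjusted, large sample: k²(A - rho²)
- Difference: (1 - k·rho)², that is (1 - slope)², since the slope is k·rho. It is zero only at slope 1.
- Cost of estimating one common slope: factor (N-3)/(N-4), which is 42/41 = 1.024 at N = 45 and 21/20 = 1.050 at N = 24. Between-patient error degrees of freedom go from 43 to 42 at N = 45.

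**Worked case, k = 1, rho = 0.5.** A = (1 + 2.5)/6 = 0.583. Change score: 0.583 + 1 - 1 = 0.583. Adjusted: 0.583 - 0.25 = 0.333. Ratio: 0.333/0.583 × 1.024 = 0.585.

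**Adjusted variance / change-score variance, N = 45, m = 6**

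| Follow-up SD / baseline SD | rho 0.3 | rho 0.5 | rho 0.7 | rho 0.9 |
|---|---|---|---|---|
| 0.7 | 0.21 | 0.29 | 0.34 | 0.28 |
| 1.0 | 0.41 | 0.59 | 0.76 | 0.94 |
| 1.5 | 0.73 | 0.95 | 1.02 | 0.68 |
| 2.0 | 0.91 | 1.02 | 0.89 | 0.41 |

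The equal-SD row corresponds to standard errors about 36%, 24%, 13% and 3% smaller (one minus the square root of the ratio). With m = 5 and equal SDs the ratios are 0.43, 0.60, 0.77 and 0.94. Simulation of 20,000 trials at equal SDs gave 0.41, 0.58, 0.76 and 0.94.

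**Other contrasts.** For the difference at a single week, with a common slope and equal SDs, simulation gave 0.66, 0.75, 0.86 and 0.97. For group-by-week contrasts, such as week 6 minus week 1, a common-slope baseline term cancels and the two analyses give the same estimate.

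**When the slope differs by arm.** Take residual SD 0.5 and baseline SD 1. With 1:2 allocation the fitted common slope sits near p = (15·b_placebo + 30·b_curcumin)/45. The large-sample variances are

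- change score: (1 - b_placebo)²/15 + (1 - b_curcumin)²/30 + 0.25 × 0.1
- adjusted: (b_placebo - p)²/15 + (b_curcumin - p)²/30 + 0.25 × 0.1

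For assumed slopes 1.1 (placebo) and 0.7 (curcumin), p = 0.833. The variances are 0.0287 and 0.0303, ratio 1.06, or 1.08 after the 42/41 factor. Simulation gave about 1.09 here, 1.15 at slopes 1.2/0.6 and 1.22 at 1.3/0.5.

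**When the slope differs by week.** With rho 0.7 and follow-up SD rising from 1.0 to 2.0 times baseline over six weeks, a common slope gave single-week ratios of 1.08 at week 1 and 1.04 at week 2.

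**The case against.** The strongest reply is that nothing in the plan is wrong. Change scores are valid in a randomized comparison, no objective names a between-arm cytokine contrast (objective 1.2.4 correlates cytokines with quality of life), no decision rests on it, and every ratio above depends on assumed correlations and spreads. If the interest is in group-by-week, adjustment with a common slope changes nothing. All of this stands. It limits the point to a possible gain in precision and gives no reason to leave the covariate out.

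Three stronger readings are tempting and are not supported.

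- **That the loss can never exceed 2.4% or 5.0%.** Those ceilings need one slope shared by both arms and, for single-week differences, by all weeks. The documents do not establish that, and the assumed cases above exceed them. Week-specific slopes would deal with the second problem but use more than one degree of freedom.
- **That radiation is known to alter the spread of serum cytokines, so a slope away from 1 can be expected.** Section 2.0 says of the NF-κB pathway "The effector proteins include acute phase reaction proteins, cytokines, adhesion molecules and feedback regulatory proteins", but this describes a mechanism and says nothing about the variance of serum levels. If spread did widen, the rows for 1.5 and 2 times baseline would apply; at rho 0.5 to 0.7 they show little or no gain.
- **That the week-averaged difference is the intended main contrast.** Section 13.0 names none. Choosing one is a separate decision about the estimand.

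**Conclusion.** The point holds as a cheap improvement of low severity. The planned analysis is unbiased but fixes the baseline slope at 1 when a baseline covariate could estimate it. Under equal SDs, six visits, compound symmetry and full participation at 15 v 30, the adjusted variance of the week-averaged arm effect is 0.41 to 0.94 of the change-score variance for correlations 0.9 down to 0.3 read in reverse, that is, the gain is largest at low correlation. It is small or absent where the slope is near 1, for example with follow-up SD 1.5 to 2 times baseline at rho 0.5 to 0.7 (ratios 0.89 to 1.02).

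Under a common slope the downside is about 2.4% of variance at 45 patients, or 5.0% at an assumed 24 (8 v 16, as after a first-stage stop). If slopes differ by arm under the 1:2 allocation, the loss was about 9% to 22% in the assumed cases. The true gain or loss cannot be fixed from the documents. This is an exploratory secondary analysis, and the pCR decision rule is untouched.

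**What to change.** Replace the sentence in section 13.0 with: *We will compare cytokine levels between treatment groups using a repeated measures model with the baseline level as a covariate.*

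The boxplots of change can stay as description. The cost is one sentence of text and about one degree of freedom, with no new samples, visits or patients. Stating it in advance also avoids a later choice between adjusted and unadjusted results.

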7.0 Evaluation During Study

During chemoradiation therapy, the patients will be assessed as follows:

- 7.1 Blood chemistries (bilirubin, alkaline phosphatase, ALT, AST, BUN, creatinine, phosphorus, calcium, glucose, total protein, albumin, and electrolytes [sodium, potassium, carbon dioxide, and chloride], and complete blood count (CBC: hemoglobin, hematocrit, WBC with differential blood cell counts (neutrophils, bands, lymphocytes, monocytes, eosinophils, basophils) and platelets) every week. Phenytoin levels will be checked in patients on phenytoin.
- 7.2 Weekly port-films
- 7.3 Weekly MDASI-GI and BFI questionnaires
- 7.4 Weekly blood collection for cytokine analysis
- 7.5 During week 2 (after at least 5 fractions of radiation therapy) of chemoradiation therapy:
 - a) Optional endoscopic biopsy

b) Optional blood collection for pharmacology (1 hour before and 1 hour after intake of curcumin or placebo)

7.6 Patients will be assessed by physician and research nurse at least once every 5 radiation fractions or as needed +/- 1 or 2 radiation fractions

Six-twelve weeks after chemoradiation therapy, patients will be restaged as follows:

7.9 Blood chemistries (bilirubin, alkaline phosphatase, ALT, AST, BUN, creatinine, phosphorus, calcium, glucose, total protein, albumin, and electrolytes [sodium, potassium, carbon dioxide, and chloride], complete blood count (CBC: hemoglobin, hematocrit, WBC with differential blood cell counts (neutrophils, bands, lymphocytes, monocytes, eosinophils, basophils and platelets), and CEA.

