7.10 MDASI-GI and BFI questionnaires

7.11 Blood collection for cytokine analysis

7.12 Study Calendar:

Tests & Procedures	Pre-treatment	During chemo-radiation	Week #2 of chemo-radiation	6-12 weeks after chemo-radiation (restaging)	Follow-up (5)
H&P; KPS	x (1)	weekly		x	
CBC (see 6.1)	x (1)	weekly		x	
Serum chemistries (see 6.1)	x (1)	weekly		x	
CEA	x (1)			x	
Phenytoin level (patients on phenytoin)	x (1)	weekly			
PT, INR (patients on coumadin)	x (1)	weekly		x	
Urinalysis	x (1)				
Urine pregnancy test (see 6.1)	x (2)				
Abd-Pelvic CT	x(3)				
Flexible sigmoidoscopy/EUS	x (3)				
Endoscopic ultrasound biopsy	x		x (6)		
CXR	x (3)				
Colonoscopy	x (4)				
MDASI, BFI	x	weekly	x	x	
Cytokines (see 9.2) (6)	x	weekly	x	x	
Pharmacology (see 9.1) (6)			x		
Telephone call (toxicity check)					x

(1) Within 15 days of enrollment
 (2) Urine pregnancy test within 72 hours of enrollment, women of child bearing age only
 (3) Within 30 days of enrollment
 (4) Within 3 months of enrollment

- (5) Telephone call 1 month +/- 1 week after last dose of curcumin/placebo.
- (6) Optional

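### The between-arm cytokine comparison uses a repeated-measures ANOVA on optional weekly draws with no rule for missing samples; run in its classical form, it keeps only patients with every draw, where a mixed model would use all samples

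*Combined protocol and SAP*

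**What the plan says.** Section 13.0 (Quality of Life and Toxicity) gives one inferential method for cytokines by arm: "We will also compare changes from baseline in cytokine levels between treatment groups using a repeated measures analysis of variance model". It adds boxplots by arm and time. It states no covariance structure, estimation method, effect measure or handling of missing samples.

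Section 9.2.1 sets the schedule: "Blood will be collected in lavender top tubes at study initiation and weekly during chemoradiation for cytokine analyses". The heading of Section 9.2 and footnote 6 of the study calendar make the cytokine work optional. Sections 6.1.2.3 and 7.4 list the same draws without that label (7.4: "Weekly blood collection for cytokine analysis"). Section 7.11 and the calendar add a draw at restaging, which is not among the evaluation times in Section 13.0.

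For quality of life, Section 13.0 plans correlations between cytokine levels and instrument scores, and for the arms: "We will also construct side-by-side boxplots of changes from baseline of QoL instrument scores by treatment group for each evaluation time". The only quality-of-life objective, 1.2.4, asks for the correlation with cytokines.

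**The concern.** Classical repeated-measures ANOVA works on a full row of visits per patient, so one missed draw removes the patient and all of that patient's other samples. With at most 15 placebo patients, there is little to spare.

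The protocol itself provides ways for draws to be missed. Treatment is interrupted for toxicity (5.2.7, 5.3.1.3). Patients go off study after two consecutive missed appointments (10.1). Treatment can end for irreversible toxicity or by patient choice (10.2).

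Two things are at stake. The first is precision. The second is bias: an analysis of complete rows is safe if missingness depends only on arm or on modelled covariates. It is doubtful if patients with toxicity miss more draws and their inflammatory cytokines also follow a different course. A likelihood-based model keeps partial rows and needs only that missingness be explained by the observed data.

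**Working it through.** **Stated figures.** The documents give no sample size, power or missing rate for the cytokine analysis, so there is no figure to reproduce on this point. The nearest stated figures do reproduce. The two-stage rule for the curcumin arm (at least 3 of 16, then at least 9 of 30) gives a significance level of 0.0746 and a power of 0.801. The downstaging comparison of 15 against 30 patients gives a power of 0.815 at two-sided 0.05. The stated values are 7.5%, 80% and 82%.

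**Inputs.**
- Arms: 15 placebo and 30 curcumin, a maximum of 45 (Section 13.0).
- Draws: 28 daily fractions (5.2.5) at 5 per week is 28/5 = 5.6 weeks, so 5 or 6 weekly draws plus baseline. I use K = 7 (baseline + 6).
- Assumed, not in the documents: a missing rate per draw of m = 5%, 10% or 20%; misses either independent or clustered within patient with intraclass correlation (ICC) 0.5; compound symmetry with correlation ρ = 0.5.

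**Complete rows.**
- Independent: (1 − m)^7.
- Clustered (beta-binomial): with s = 1/ICC − 1 = 1, the product over i = 0 to 6 of [s(1 − m) + i] / (s + i).

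**Standard-error ratio, complete rows against all samples.** A patient with k observed changes from baseline carries information I(k) = 1/[ρ + (1 − ρ)/k]. With p_k the probability of observing k of the 6 post-baseline draws, the ratio is √{Σ p_k I(k) / [p_6 I(6)]}. Six draws enter here rather than seven because a patient without a baseline has no change from baseline under either method.

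Example, independent, m = 10%: p_6 = 0.9^6 = 0.531 and I(6) = 1/(0.5 + 0.5/6) = 1.714, with product 0.911. The sum over all k is 1.683. The ratio is √(1.683/0.911) = 1.36.

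| m (assumed) | Independent: share complete | of 45 | of 15 placebo | SE ratio | Clustered: share complete | of 45 | SE ratio |
|---|---|---|---|---|---|---|---|
| 5% | 0.698 | 31 | 10 | 1.16 | 0.877 | 39 | 1.05 |
| 10% | 0.478 | 22 | 7 | 1.36 | 0.765 | 34 | 1.11 |
| 20% | 0.210 | 9 | 3 | 1.91 | 0.576 | 26 | 1.23 |

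**Sensitivity.**
- Varying ρ from 0.3 to 0.7 barely moves the independent ratios: 1.16, 1.35 to 1.37, and 1.88 to 1.93.
- With independent misses, K = 6 leaves about 33, 24 and 12 complete rows; K = 8 (restaging included) leaves about 30, 19 and 8 (7.5).
- At m = 2%, independent, K = 7, about 39 of 45 remain and the loss is small.

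**Detectable difference for one contrast** (assumed two-sided 0.05 and 80% power): (1.96 + 0.84)·√[1/n + 1/(2n)], with n the placebo patients used.
- No missing data, n = 15: 0.89 SD.
- Complete rows, independent misses, n = 15(1 − m)^7: 1.06, 1.28 and 1.93 SD at m = 5%, 10% and 20%.
- All patients with baseline and that visit, n = 15(1 − m)^2: 0.93, 0.98 and 1.11 SD.

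The normal approximation is rough at the smallest n.

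**The case against.** The strongest reply is that Section 13.0 does not mention deletion. The term used there can also cover a likelihood-based repeated-measures model, which keeps partial rows. That is right. A reader might infer that the plan discards every patient with one missing sample, and the documents do not support it. The exclusion from analysis in 10.1 concerns patients who fail to complete protocol therapy for reasons other than toxicity or progression, not patients who miss a sample. What stands is that the plan leaves the choice open and that the classical reading is the costly one.

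A reader might also infer that quality of life gets only boxplots. That is true of the comparison between arms alone. The planned correlations answer objective 1.2.4, and no objective asks for a quality-of-life comparison by arm.

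The size is open to challenge too. The labelling of the draws as optional may mean that a patient declines altogether; such a patient gives no samples, and no model recovers them. Participants already have weekly visits and blood work (7.1, 7.6), and nothing says that draws stop while a drug is held. Clustered misses are therefore plausible, and they shrink the loss considerably, as the table shows.

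Finally, the mixed model does not dispose of toxicity-related gaps. A model with arm and week has no toxicity term, so missing-at-random holds only if the observed cytokine values explain the missingness.

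**Conclusion.** The point holds as a weakness in the choice and specification of the method. The named method, in its usual form, is poorly suited to optional weekly samples in arms of 15 and 30, and a better one is available for the same data.

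The standard-error penalty is between about 1.05 and 1.9 times, depending on a missing rate (5% to 20%) and a pattern of misses (clustered or independent), both of which are assumptions. If few draws are missed, or if the sponsor already intends a likelihood-based model, there is little or no loss and one sentence settles the matter.

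The comparison is secondary, with no stated alpha or power, and it does not enter the pCR decision rule. The change should be made, but the main conclusion of the trial does not depend on it.

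**What to change.** Replace the sentence in Section 13.0 with a likelihood-based linear mixed model for repeated measures:
- fixed effects for arm, week and arm by week;
- a stated within-patient covariance structure;
- all available samples, with a statement of what happens to a patient without a baseline sample;
- small-sample degrees of freedom, for example Kenward-Roger;
- the arm effect reported with a 95% CI.

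State that the model assumes missing-at-random, and tabulate the number of samples by arm and week with reasons for gaps, so that toxicity-related missingness can be seen.

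In the same edit, reconcile the optional label (9.2 and the calendar) with 6.1.2.3 and 7.4, and say whether the restaging draw belongs to the analysis. State that quality of life by arm is descriptive; an estimate with a 95% CI beside the boxplots would be an optional addition.

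The cost is wording only, with no extra patients, visits or samples.
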